14.6. Future Use of Stored Specimens and Other Identifiable Data	51
15. DATA HANDLING AND RECORD KEEPING.....	51
15.1. Management of Banked Samples	52
15.2. Data Management Responsibilities.....	52
15.3. Data Capture Methods.....	53
15.4. Types of Data	53
15.5. Schedule and Content of Reports	53
15.6. Study Records Retention	53
15.7. Protocol Deviations.....	53
16. PUBLICATION/DATA SHARING.....	54
17. REFERENCES.....	54
APPENDIX A: SCHEDULE OF EVENTS	A
APPENDIX B: CEREBROVASCULAR ACCIDENT ADVERSE EVENT MANAGEMENT ALGORITHM FOR THE COMBINATION OF BEMPEGALDESLEUKIN WITH CHECKPOINT INHIBITORS.....	C
APPENDIX C: HYDRATION GUIDELINES	D

LIST OF ABBREVIATIONS

AE	Adverse Event/Adverse Experience
ALT	Alanine aminotransferase
ANC	Absolute Neutrophil Count
AST	Aspartate aminotransferase
BUN	Blood Urea Nitrogen
CB	Clinical Benefit
CBC	Complete Blood Count
CFR	Code of Federal Regulations
CMP	Comprehensive Metabolic Panel
CNS	Central Nervous System
CoC	Certificate of Confidentiality
CR	Complete Response
CRCO	Clinical Research Central Office
CTCAE	Common Terminology Criteria for Adverse Events
CTV	Clinical Target Volume
CVA	Cerebrovascular Accident
DCR	Disease Control Rate
DHHS	Department of Health and Human Services
DOAC	Direct Oral Anticoagulation
DOT	Disease Oriented Team
DSMC	Data and Safety Monitoring Committee
EBRT	External Beam Radiation Therapy
ECOG	Eastern Cooperative Oncology Group
eCRF	Electronic Case Report Form
EQD2	Equivalent Dose in 2 Gy Fractions
FDA	Food and Drug Administration
FFPE	Formalin Fixed Paraffin Embedded
FFR	Federal Financial Report
GCP	Good Clinical Practice
GTV	Gross Tumor Volume
Hgb	Hemoglobin
HHS	Health and Human Services
HIPAA	Health Insurance Portability and Accountability Act
HIV	Human Immunodeficiency Virus

HNSCC	Head and Neck Squamous Cell Carcinoma
HRQoL	Patient-reported Health-Related Quality of Life
IB	Investigator's Brochure
ICH	International Council for Harmonization
IFN	Interferon
IME	Important Medical Event
IMRT	Intensity Modulated Radiation Therapy
IND	Investigational New Drug Application
INR	International Normalized Ratio
IRB	Institutional Review Board
IV	Intravenous
LMWH	Low Molecular Weight Heparin
MHC	Major Histocompatibility Complex
MOS	months
MTD	Maximum Tolerated Dose
N	Number (typically refers to participants)
NKTR-214	Bempegaldesleukin
OHRP	Office for Human Research Protections
ORR	Overall Response Rate
OS	Overall Survival
PBMC	Peripheral Blood Mononuclear Cells
PD	Progressive Disease
PD-1	Programmed death one
Anti-PD1	Anti-program death one
PEG	Polyethylene glycol
PFS	Progression-free Survival
PHI	Protected Health Information
PI	Principal Investigator
PR	Partial Response
PRC	Pharmaceutical Research Center
PSR	Protocol Summary Reports
PTV	Planning Target Volume
RECIST	Response Evaluation Criteria in Solid Tumors
RT	Radiation Therapy
SAE	Serious Adverse Event/Serious Adverse Experience
SD	Stable Disease

SOC	Standard of Care
SOP	Standard Operating Procedure
ULN	Upper Limit of Normal
UP	Unanticipated Problem
UW	University of Wisconsin
UWCCC	University of Wisconsin Carbone Cancer Center
WBC	White Blood Cell
WOCBP	Women of Childbearing Potential

PROTOCOL SUMMARY

Title: *Phase II Study of Bempegaldesleukin (NKTR-214) Together with Palliative Radiation and anti-PD-1 Checkpoint Blockade in Patients with Recurrent or Metastatic Head and Neck Squamous Cell Carcinoma*

Précis: This is a Phase II study of NKTR-214 in combination with palliative radiation and anti-PD-1 checkpoint blockade in patients with recurrent or metastatic head and neck cancer. For all enrolled participants, cycle 1 consists of anti-PD-1 therapy and NKTR-214, followed by palliative radiation combined with anti-PD-1 therapy and NKTR-214 in cycle 2. In subsequent cycles participants will receive NKTR-214 and anti-PD-1. Participants who have one or more sites in need of palliative radiation therapy who have not received previous PD-1 directed therapy are eligible. The phase II study will enroll 24 subjects with a primary endpoint of overall response rate.

Objectives:

Primary Objective:

- Evaluate the objective response rate (ORR) to NKTR-214 in combination with anti-PD-1 therapy and palliative radiation in the efficacy-evaluable population.
 - *Outcome measure:* ORR will include confirmed complete response (CR) + confirmed partial response (PR) and will be determined as per RECIST1.1, by investigator assessment.

Secondary Objectives:

- Determine the safety, as well as, the progression free survival (PFS), overall survival (OS), clinical benefit (CB, defined as CR + PR + stable disease at \geq 6 months (SD)), and duration of response with NKTR-214, anti-PD-1, and palliative radiation in the efficacy-evaluable population
- *Outcome measures:*
 - Toxicities \geq Grade 3 is defined by the NCI Common Terminology Criteria for Adverse Events (CTCAE) version 5.0. Toxicities not "unrelated" to treatment, will be considered treatment-related.
 - PFS is defined as the time from D1 of treatment until the criteria for disease progression is met as defined by RECIST1.1 or death as a result of any cause.
 - OS is defined as time from D1 of treatment until death as a result of any cause.
 - CB will include confirmed complete response (CR) + confirmed partial response (PR) + stable disease at \geq 6 months (SD) and will be determined as per RECIST1.1.
 - Duration of response is the period measured from the time that measurement criteria are met for complete or partial response (whichever status is recorded first) until the date that recurrent or progressive disease is objectively documented.
- Determine the impact of NKTR-214, palliative RT, and anti-PD-1 therapy on patient-reported health-related quality of life (HRQoL)
 - *Outcome measures:* Patient-reported HRQoL will be monitored to evaluate participant tolerance of treatment using EORTC QLQ-C30, EORTC QLQ-H&N35, and EQ-5D. These will be administered at baseline; 7 days after cycle 1 and cycle 2; then every 12 weeks to the end of treatment + once more at 30 days post treatment. HRQoL will be analyzed in pts who received \geq 1 dose of study drug and have \geq 1 HRQoL assessment.

Exploratory Objectives:

- Evaluate each subject's tumor expression of PD-L1 by histology (using anti-PD-L1 clone 22c3 – standard in UW Surgical Pathology) and determine whether this predicts response to NKTR-214, palliative RT, and anti-PD-1 therapy
- Evaluate the immunologic activation induced by NKTR-214, palliative RT, and anti-PD-1 using serologic and flow cytometry immune assays and T cell receptor sequencing
- Evaluate for histological evidence of antitumor activity based on the cellular phenotype of infiltrate

Population:	24 adult patients of any gender, race or ethnicity, age ≥ 18 with Eastern Cooperative Oncology Group (ECOG) Performance Status 0-2 and a biopsy-proven recurrent/metastatic head and neck squamous cell carcinoma who are taking or will be starting anti-PD-1 therapy and have a need for palliative radiation will be eligible for this study.
Phase:	Phase II
Number of Sites:	1
Description of Intervention:	
Following an informed consent process, the subjects will receive anti-PD-1 therapy with 200 mg of pembrolizumab and NKTR-214 at 0.006 mg/ml. Palliative radiation therapy will then be delivered to tumor sites causing or felt by the treating physician to have a high potential for causing symptoms with either 8 Gy X 3 or 4 Gy X 5 completed 3 to 7 days prior to cycle 2 of anti-PD1 and NKTR-214. Combined anti-PD-1 and NKTR-214 will then be delivered each subsequent cycle.
 
This trial will evaluate safety and efficacy of the combination of anti-PD1, NKTR-214, and palliative radiation therapy in patients with recurrent or metastatic squamous cell carcinoma of the head and neck. Twenty-four participants will be enrolled to evaluate the efficacy of this combination. Efficacy will be measured by ORR, PFS, OS, CB, and duration of response with ORR the primary outcome being compared to historical control data. Toxicity will be evaluated prior to administration of each cycle, while receiving NKTR-214 followed by every four months after the participant is off trial. Health related quality of life questionnaires will be completed with cycle 1 and 2 and then every 4 cycles thereafter.

Study Duration:	36 months
Estimated Mean Duration of Subject Participation:	9 months

Estimated Time to Complete Enrollment: 27 months

Schematic of Study Design:

Screen patients with biopsy-proven recurrent/metastatic head and neck squamous cell carcinoma who are taking or will be starting anti-PD-1 therapy and have a need for palliative radiation. Verify eligibility. Obtain informed consent and history, document.

Cycle 1 (21 days)
Pembrolizumab and NKTR-214 (Day 1)

Cycle 2 Day -3 to -7
Complete palliative radiation therapy

Cycle 2+
Pembrolizumab and NTRK-214

KEY ROLES AND CONTACT INFORMATION

Study co-chairs: (with ultimate responsibility for conduct and oversight of the study)	[name], PhD IND Sponsor UW Carbone Cancer Center, Radiation Oncology Vice-Chair, Department of Human Oncology University of Wisconsin School of Medicine and Public Health [name] [contact] [contact]
	[name] Department of Human Oncology University of Wisconsin School of Medicine and Public Health [name] [contact] [contact]

1. INTRODUCTION: BACKGROUND INFORMATION AND SCIENTIFIC RATIONALE

1.1. Background Information

1.1.1. *Recurrent/Metastatic Head and Neck Squamous Cell Carcinoma*

Concurrent or induction chemotherapy used with radiation therapy (RT) has the potential to cure some patients diagnosed with locoregional head and neck squamous cell carcinoma (HNSCC). However, many patients will relapse with locoregional recurrent disease or metastatic spread. The median survival for patients with recurrent or metastatic HNSCC is 6-12 months (1). Some of these patients are candidates for salvage therapy with intent to cure using surgery or re-irradiation. Most, however, will ultimately require systemic palliative therapy.

1.1.2. *Checkpoint Inhibitor Immunotherapy in Metastatic Head and Neck Cancer*

Prior to publication of Keynote-048, anti-PD-1 checkpoint inhibition was reserved for patients with recurrent or metastatic disease that was refractory to first line platinum agents. Keynote-048 demonstrated non-inferiority of anti-PD-1 monotherapy to the previous standard of care cetuximab, platinum, and 5-FU in the overall study population and demonstrated a 17 % ORR to pembrolizumab alone in patients with metastatic or recurrent HNSCC (2). This has resulted in approval of anti-PD-1 monotherapy with pembrolizumab for patients with combined positive score for PD-L1 of greater than or equal to one. Both nivolumab and pembrolizumab are approved following progression on platinum containing chemotherapy. Nivolumab and pembrolizumab are checkpoint inhibitors that bind PD-1 surface molecules on immune cells and antagonize the interactions of PD-1 with PD-L1. In healthy individuals, this PD-1/PD-L1 interaction suppresses the immune system, thereby preventing autoimmune disease. HNSCC and other tumor types utilize PD-L1 expression as a means to evade immune surveillance and turn off an anti-tumor immune response. Nivolumab and pembrolizumab block the PD-1/PD-L1 interaction in the tumor microenvironment, effectively “taking the breaks off” the immune system.

1.1.3. *NKTR-214 in Combination with Anti-PD-1 Following Palliative Radiation*

Preclinical and clinical studies demonstrate a cooperative interaction between radiation and anti-PD-1 checkpoint blockade (3). In this context, radiation can function as a method of in situ tumor vaccination resulting in enhanced dendritic cell maturation, antigen cross-presentation, and diversification of the anti-tumor T cell response. A Phase II clinical trial (MSKCC 15-253) delivered combined anti-PD-1 checkpoint blockade together with radiation in patients with recurrent/metastatic HNSCC. Early results did not indicate any excess toxicity with this combination (11 % incidence of treatment related toxicity \geq Grade 3). That study demonstrated an overall response rate of 22 % and median PFS of 2.4 mos with radiation and anti-PD-1 therapy in patients with metastatic or recurrent HNSCC.

Bempegaldesleukin (NKTR-214), a novel cytokine with enhanced immune system activation, has the potential to be an important advancement for the treatment of patients with cancer. NKTR-214 consists of IL2, which has the same amino acid sequence as aldesleukin, conjugated at a defined region within the protein to releasable polyethylene glycol (PEG) chains. The PEG chains render the molecule inactive. After administration in vivo, the PEG chains are slowly hydrolyzed to generate active cytokine conjugates. This affords a superior safety profile for NKTR-214 compared to IL2, allowing for outpatient administration and a longer duration of action requiring less frequent dosing. The most active IL2 conjugates are 2-PEG-IL2 and

1-PEG-IL2. The location of the PEG chains on the active conjugated-IL2 reduces its affinity to the IL2 receptor alpha subunit (IL2Ra), responsible for activating undesirable Treg cells to a greater extent than affinity to the IL2-receptor beta subunit (IL2Rb) (4, 5). In the tumor, NKTR-214 preferentially activates CD8+ T cells and natural killer (NK) cells over Treg cells and provides sustained exposure to active 1-PEG and 2-PEG-IL2 (6).

Preclinical data from our group and others suggests a synergistic interaction between NKTR-214 and radiation (7). In this combination, radiation acts as a “spark” by inducing neoantigen presentation by tumor cells on MHC-I, increased IFN- γ production, and improved antigen presentation (8). NKTR-214 helps to exploit these immunologic changes at the tumor by increasing tumor infiltrating lymphocytes (mainly CD4 and CD8 T cells) and NK cells (5). The combination has repeatedly been shown to be effective in preclinical syngeneic murine tumor models where neither treatment alone is sufficient to decrease tumor burden, but combined radiation and NKTR-214 result in decreased tumor burden and ~80 % of the mice become disease free.

In a recent clinical study (PIVOT-02), NKTR-214 demonstrated safety in combination with anti-PD-1 checkpoint blockade. Grade 3 or 4 treatment-related adverse events (AEs) were observed in 5.7 % of patients receiving NKTR-214 dose at or below 0.006 mg/kg plus anti-PD-1 checkpoint blockade. At a higher NKTR-214 dose 0.009mg/kg with anti-PD-1 blockade, two patients experienced dose limiting toxicity in the form of hypotension and metabolic acidosis. There were no patient discontinuations due to treatment-related AEs and no treatment-related deaths. Based off the PIVOT-02 toxicity results, we have decided to forgo a traditional 3+3 dose escalation study exploring the toxicity of NKTR-214 in combination with anti-PD-1 following palliative radiation. Instead, we propose to test the safety and efficacy of the MTD dose of the PIVOT-02 trial (0.006 mg/kg NKTR-214) in combination with palliative radiation and anti-PD-1 therapy.

The PIVOT-02 trial also demonstrated NKTR-214 in combination with anti-PD-1 is effective in mounting an anti-tumor immune response. This combination (0.006 mg/kg NKTR-214 + 360 mg Nivolumab q3w) has shown efficacy in patients with Stage IV melanoma [ORR 50 %, disease control rate (DCR) 71 %], Stage IV renal cell carcinoma (ORR 46 %, DCR 77 %), and Stage IV non-small cell lung carcinoma (ORR 75 %, DCR 75 %) (9, 10).

1.2. Rationale

Based on the available clinical data and preclinical data, we hypothesize that the combination of palliative radiation, NKTR-214, and anti-PD-1 checkpoint blockade will improve the ORR compared to a 22 % estimated ORR (based on historical data outlined above) for pembrolizumab alone or pembrolizumab plus palliative radiotherapy in patients with metastatic or recurrent HNSCC. Given the non-redundant and potentially synergistic immunologic effects of radiation, NKTR-214, and anti-PD-1 checkpoint blockade, our primary hypothesis is that this combination will be effective in generating an anti-tumor immune response against recurrent/metastatic HNSCC resulting in ≥ 44 % ORR. We further anticipate a rate of ≤ 25 % unexpected grade 3 toxicity with good patient-reported HRQoL and with correlative evidence demonstrating a more diversified and activated adaptive anti-tumor immune response. Because many side effects related to IL2 based therapies are predictable, transient, and manageable, they should not limit the evaluation of overall safety or therapeutic efficacy.

1.3. Potential Risks and Benefits

1.3.1. *Potential Risks*

NKTR-214

The potential AEs of NKTR-214 have been assessed in recent clinical studies and commonly include: fatigue, flu-like symptoms, rash, fever, pruritus, hypotension, decreased appetite, arthralgia, and cough. Flu-like symptoms, rash and pruritus are assumed to be cytokine mediated and have occurred 3-4 days after treatment. These were mild to moderate in severity. Other possible risks include, anemia, periorbital edema, cerebrovascular accident, atrial fibrillation and tachycardia, abdominal pain, constipation, diarrhea, nausea, weight decrease, myalgia, dizziness, headache, syncope, anxiety, dyspnea, dysphonia, and pleural effusion.

SAEs of cerebrovascular accident (CVA), including one fatal event, have been observed in patients who have received NKTR 214 in the triplet combination with nivolumab and ipilimumab and in the doublet combination with nivolumab. A comprehensive search (data cutoff 21 June 2019) found 3 of 43 patients (7 %) who received triplet therapy in Study 16-214-02 (PIVOT-02) to have CVA events, all of which were considered by the investigator to be related to treatment with bempegaldesleukin, nivolumab, and ipilimumab. Additionally, 8 of 478 patients (1.7 %) who received doublet therapy (bempegaldesleukin and nivolumab) in Study 16-214-02 had CVA events, which were considered by the investigator to be related to treatment with bempegaldesleukin and nivolumab in 3 patients, to nivolumab in 1 patient, and unrelated to treatment in 4 patients. The relationship of these events to the triplet and doublet combinations is unclear. Based on these events and a comprehensive assessment of CVA across all NKTR-214 clinical studies, CVA has been escalated to an adverse event of special interest (AESI) and mitigations have been put in place to reduce the risk of CVA. These mitigations include implementation of a CVA AESI management algorithm (Appendix B) and updates to the exclusion criteria, renal function and hydration assessment, hydration guidelines, concomitant and prohibited medications, dose modification guidelines, and discontinuation criteria. Additional information on the clinical safety and risk of CVA is found in the NKTR-214 Investigator's Brochure (IB).

There is also the risk that previously unidentified AE could occur, as this is an investigational agent.

Anti- PD-1

The side effects of anti- PD-1 therapy are well described and are similar between nivolumab and pembrolizumab. The most common side effects reported in \square 20 % of patients were fatigue, pruritus, diarrhea, decreased appetite, rash, dyspnea, constipation, and nausea. Other serious but less common side effects were immune related pneumonitis, colitis, hepatitis, endocrinopathies (including hypophysitis thyroid disorders and type I diabetes mellitus), nephritis, infusion reactions, and embryonal toxicities.

Palliative radiation therapy

The side effects related to radiation therapy will vary by the site in need of palliative radiation therapy. They are well known but are listed here to distinguish between those related to NKTR-214. Within the head and neck region, common side effects include: mucositis, difficulty swallowing which may necessitate a feeding tube, dry mouth, change in taste and smell, reduced saliva production, hoarseness, radiation dermatitis, ear pain/infection, hearing loss, fatigue, weight loss, dehydration requiring IV fluids and electrolyte replacement, hair loss, tooth decay, decreased thyroid function. Rare and serious side effects include: breathing and swallowing issues that require a tracheotomy, nerve damage in the head and neck region, radiation necrosis of the jaw, damage to the larynx or nerves, damage to the skin, soft tissues or other parts of the head and neck that may require a surgery to correct and damage to the spinal cord which may cause permanent weakness.

Outside of the head and neck, side effects vary by body region. Within the thorax, common side effects include esophagitis, dry cough, and fatigue. Esophagitis may require gastrostomy tube placement. Rare but significant side effects include radiation pneumonitis, radiation fibrosis, and rib fracture. Within the abdominal and pelvic regions, common side effects include diarrhea, nausea, and fatigue. Rare but significant side effects include ulcer, hemorrhage, obstruction, liver failure, renal failure, radiation cystitis, radiation proctitis, and pelvic insufficiency fracture. At extremity and skin sites, common side effects include skin reaction and fatigue. Significant effects include lymphedema and rarely non-healing wound.

Other risks from research-related procedures

- Biopsy tissue collection: primary risks include temporary discomfort, bleeding, infection, and ulceration
 - There are some risks associated with a tissue biopsy and steps will be taken to minimize these. Standard laboratory tests will be done to assess bleeding risk before the procedure is done. The sample will be taken from an area of reduced risk of complications. Possible side effects of a biopsy include bleeding, infection, bruising, pain or discomfort at the biopsy site and possible side effects from the local anesthetic (pain or bruising at the site where anesthetic is given). The main discomfort associated with this test is pain when the bone or tissue is being withdrawn. In order to make the procedure more comfortable, subjects may get a local anesthetic such as lidocaine to numb the area, at the discretion of the physician performing the biopsy. Local anaesthesia is generally very safe, however potential risks include blurred vision, dizziness, vomiting, headache, muscle twitching, continuing numbness, weakness, tingling, and allergic reaction. It is recommended that subjects be observed for at least 2 hours after the biopsy.
- CT scans for biopsies: At the time of biopsy, a CT scan may be done to determine where the biopsy will be done. After the biopsy, a CT scan may be done over the biopsy site to look for any immediate complications. These scans will be performed in addition to the scans as part of normal cancer care. The scans involve exposure to radiation in the form of x-rays. The level of radiation used is kept to a minimum to prevent damage to body cells. Under some rare circumstances of prolonged, high-dose exposure, x-rays

can cause adverse health effects, such as skin reddening (erythema), skin tissue injury, hair loss, and cataracts. The amount of radiation from the additional scans in this study is not known to be associated with any serious health risks. The exposure related to this CT scan equals approximately one year of standard environmental background radiation.

- IV fluid bolus is generally very safe, however potential risks include injury to peripheral vein, bleeding, bruising, infection at infusion site, and development of peripheral or pulmonary edema.
- Blood draws for clinical laboratory testing risks include bruising, swelling at the injection site, dizziness and lightheadedness.
- Questionnaire risk loss of confidentiality, which is possible but not likely with data security safeguards in place.

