8.1.2. Adverse Events (AEs)

An AE is any untoward medical occurrence whether or not considered related to the study drug that appears to change in intensity during the course of the study. The following are examples of AEs:

- Unintended or unfavorable sign or symptom
- A disease temporally associated with participation in the protocol
- An intercurrent illness or injury that impairs the well-being of the subject

Abnormal laboratory values or diagnostic test results constitute AEs only if they induce clinical signs or symptoms or require treatment or further diagnostic tests.

Hospitalization for elective surgery or routine clinical procedures that are not the result of an AE (e.g., surgical insertion of central line) should not be recorded as an AE.

Disease progression should not be recorded as an AE, unless it is attributable to the study regimen by the site investigator.

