8.1.3. Serious Adverse Events (SAEs)

A serious adverse event is defined as any adverse event that meets one or more of the following criteria:

- Results in death; OR
- Is life-threatening; OR
- Requires hospitalization or prolongs existing hospitalization; OR
- Results in significant or persistent disability or incapacity; OR
- Results in a congenital anomaly/birth

Planned hospitalizations for disease-related surgery, routine procedures, non-disease-related procedures, and grade 3 toxicities listed in section 2.6.1.2 are not considered SAEs.

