***Planned hospitalizations for disease-related surgery, routine procedures (such as G-tube placement), non-disease-related procedures, and grade 3 toxicities listed in section 2.6.1.2 will be exempt from SAE reporting as they are not dose limiting toxicities.**

Expedited AE reporting timelines are defined as:

- **24-Hour; 5 Calendar Days** – The AE must initially be reported within 24 hours of learning of the AE, followed by a complete expedited report within 5 calendar days of the initial 24-hour report.
- **10 Calendar Days** – A complete expedited report on the AE must be submitted within 10 calendar days of learning of the AE.

Serious adverse events that occur more than 90 days post completion of therapy, only SAEs with the attribution of possibly, probably or definitely will require reporting as follows:

Expedited 24-hour notification followed by complete report within 5 calendar days for:

- All Grade 3, 4, and 5 AEs

Expedited 10 calendar day reports for:

- Grade 2 AEs resulting in hospitalization or prolongation of hospitalization

Serious Adverse Event – Reported Within 24 Hours

Serious Adverse Events requiring reporting within 24 hours (as described in the protocol) must also be reported to the Data and Safety Monitoring Committee (DSMC) Chair via an email to [contact] within one business day. The OnCore SAE Details Report must be submitted along with other report materials as appropriate (NCI AdEERS form or FDA Medwatch Form #3500 and/or any other documentation available at that time of initial reporting). The DSMC Chair will review the information and determine if immediate action is required. Within 10 working days, all available subsequent SAE documentation must be submitted electronically along with a 24 hour follow-up SAE Details Report and a completed UWCCC SAE Routing Form to [contact]. All information is entered and tracked in the UWCCC database.

The Principal Investigator notifies all investigators involved with the study at the UWCCC, the IRB, the sponsor, and the funding agency and provides documentation of these notifications to the DSMC.

If the SAE occurs on a clinical trial in which the UW PI serves as the sponsor-investigator, the PI reviews the event to determine whether the SAE requires reporting to the FDA and other participating investigators.

For a multiple-institutional clinical trial the PI is responsible for ensuring SAEs are reported to the FDA as well as to all participating investigators.

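### The SAE exemption for planned procedure admissions names G-tube placement but omits the limit to procedures not caused by an AE, so a planned admission for a toxicity-driven tube can escape SAE reporting

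*Combined protocol and SAP*

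**What the plan says.** Section 1.3.1 (Potential Risks, palliative radiation therapy) treats tube placement as a possible result of radiation toxicity. For head and neck sites the common effects include "difficulty swallowing which may necessitate a feeding tube". For thoracic sites, "Esophagitis may require gastrostomy tube placement".

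Two places then take certain admissions out of the SAE system:

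- Section 8.1.3, after the SAE criteria: "Planned hospitalizations for disease-related surgery, routine procedures, non-disease-related procedures, and grade 3 toxicities listed in section 2.6.1.2 are not considered SAEs".
- The footnote to Table 1 in section 8.4.2, tied by an asterisk to the hospitalization criterion: "Planned hospitalizations for disease-related surgery, routine procedures (such as G-tube placement), non-disease-related procedures", together with certain Grade 3 toxicities, "will be exempt from SAE reporting as they are not dose limiting toxicities".

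Section 8.1.2 has a similar rule for AE recording, but with a limit. What need not be recorded as an AE is "Hospitalization for elective surgery or routine clinical procedures that are not the result of an AE".

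**The concern.** The rule for AEs and the rule for SAEs do not match. The AE rule leaves out a procedure admission only when no AE lies behind it. The SAE rule has no such condition, and its one named example is a procedure that the protocol's own risk section describes as a possible result of protocol radiation.

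At stake is the reporting route. Under 8.4.2, SAEs go on an expedited timeline to the DSMC and the drug supplier, and the sponsor-investigator reviews SAE reports for suspected causality and unexpectedness. Under 9.1.1, SAEs are accumulated in the quarterly Protocol Summary Report. An exempted tube admission would miss all of these as an SAE. The route carries some weight here: section 1.1.3 forgoes dose escalation for the combination, section 5.8 allows previously radiated sites to be radiated again, and section 11 contains no toxicity stopping rule.

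**Working it through.** The plan gives no figure to reproduce. The check is to follow one event through the text.

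**Event.** A participant develops dysphagia or esophagitis from protocol radiation, needs a G-tube, and has a planned admission of at least 24 hours to place it.

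1. *Is there an AE?* Yes. Section 8.1 requires all AEs, serious or not, to be recorded, and 5.8 has radiation-related AEs assessed at every follow-up where AEs are evaluated. The 8.1.2 exclusion does not apply, because the procedure results from an AE.
2. *Does it meet an SAE criterion?* Yes. It involves hospitalization (8.1.3), and the stay reaches the 24-hour threshold in Table 1, criterion 3.
3. *Does an exemption apply?* On the wording, yes. The stay is planned, and the footnote names the procedure as routine. Neither 8.1.3 nor the footnote asks why the tube was needed.
4. *Does another criterion bring it back?* Possibly. The asterisk attaches only to criterion 3. Criterion 6 of Table 1 (important medical events) can make an event serious on medical judgment. That criterion is absent from the list in 8.1.3, so this route rests on judgment and on one of two lists.
5. *Does expectedness or attribution settle it?* No. Section 8.3.2 names Grade 3 mucositis and dermatitis as the expected radiation toxicities, and neither it nor its NKTR-214 list includes dysphagia or esophagitis. Table 1 requires SAEs to be reported whether or not they are related to the investigational agent, so the standard-of-care label on radiation is no ground for omission.

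**What does not change.** Unplanned admissions for dysphagia, esophagitis or dehydration fall outside the exemption. The safety analysis in 11.3.2 is the proportion with Grade 3+ treatment-related toxicity and its 95% CI, which depends on grade and attribution, not on SAE status.

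**Scale.** With N = 24 (section 11.2), if k participants have this as their only SAE, the participant-level SAE proportion is understated by k/24:

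- k = 1: 1/24 = 4.2 percentage points
- k = 2: 2/24 = 8.3 percentage points
- k = 3: 3/24 = 12.5 percentage points

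These values of k are illustrations. The documents give no expected tube rate, and a participant with any other SAE contributes nothing to the shortfall.

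**The case against.** The strongest reply is that little is lost. Only planned stays are exempt, and the word could mean planned independently of any new event. The important-medical-event criterion may still capture a tube needed for toxicity, and Table 1 sets a timeline of 24 hours and then 5 calendar days for Grade 3 to 5 SAEs without a 24-hour hospitalization. The AE stays on the case report form. The Protocol Summary Report covers toxicities as well as SAEs (9.1.1), section 15.5 lists AEs among the contents of reports to the DSMC, and disease-team meetings discuss significant toxicities (9.1). No endpoint or stopping rule uses an SAE count.

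Most of this stands, and it limits the point to SAE status and the expedited route. It does not close the gap. The protocol never defines planned. The footnote's stated reason, that the exempted events are not dose limiting, sits poorly with a reading confined to procedures unrelated to toxicity, and the protocol sets no dose-limiting toxicity criteria. A general AE listing also does not replace expedited notice or the sponsor-investigator's review of SAE reports.

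A reader might infer that every admission caused by dysphagia or esophagitis drops out, or that the DSMC would not see the toxicity. The text supports neither. A reader might also infer that tube placement is among the likeliest serious harms of adding two immune agents to radiation. Section 1.3.1 attributes it to radiation alone, and the radiation may be given at many body sites.

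**Conclusion.** The point holds in a limited form. Followed as written, 8.1.3 and the Table 1 footnote allow a planned admission of 24 hours or more for a toxicity-driven feeding tube to be left out of expedited SAE reporting and the cumulative SAE report, unless the event is serious on another criterion.

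The size is 4.2 percentage points of the participant-level SAE proportion for each affected participant with no other SAE. It is tempting to assume a tube rate and convert it into a count of missing SAEs. The documents support no such rate. Any such count would also be an upper bound, because it assumes that every tube involves a planned stay of at least 24 hours and meets no other criterion. The primary analysis and the planned toxicity analysis are unaffected. This is a reporting rule that should be corrected, not evidence that harm is concealed.

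**What to change.** Reconcile 8.1.2, 8.1.3 and the Table 1 footnote. In both SAE exemptions, add the limit already used in 8.1.2, so that a planned procedure admission is exempt only when the procedure does not result from an AE. Apply the same condition to the G-tube example. State what planned means.

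A cut-off such as planned before C1D1 is not needed. It could turn later tube placements for tumor-related dysphagia into SAEs, although 8.1.2 keeps disease progression out of AEs unless it is attributed to the regimen.

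The same sentences cite a section 2.6.1.2 that this protocol does not contain. That is a separate defect, but one edit can correct both.

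The cost is one clause in two places and a few more SAE reports. Treatment, sample size and analyses do not change.
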